11. MEASUREMENT OF EFFECT

11.1 Antitumor Effect – Solid Tumors

For the purposes of this study, patients should be re-evaluated for response at the end of radiation within 8 weeks of the completion of radiation.

Response and progression will be evaluated in this study using the new international criteria proposed by the revised Response Evaluation Criteria in Solid Tumors (RECIST) guideline (version 1.1) [31]. Changes in the largest diameter (unidimensional measurement) of the tumor lesions and the shortest diameter in the case of malignant lymph nodes are used in the RECIST criteria.

11.1.1 Definitions

Evaluable for toxicity. All patients will be evaluable for toxicity from the time of their first treatment with cisplatin.

Evaluable for objective response. Only patients who have measurable disease present at baseline, have received at least one cycle of therapy, and have had their disease re-evaluated will be considered evaluable for response. These patients will have their response classified according to the definitions stated below. (Note: Patients who exhibit objective disease progression prior to the end of cycle 1 will also be considered evaluable.)

Evaluable Non-Target Disease Response. Patients who have lesions present at baseline that are evaluable but do not meet the definitions of measurable disease, have received at least one cycle of therapy, and have had their disease re-evaluated will be considered evaluable for non-target disease. The response assessment is based on the presence, absence, or unequivocal progression of the lesions.

11.1.2 Disease Parameters

Measurable disease. Measurable lesions are defined as those that can be accurately measured in at least one dimension (longest diameter to be recorded) as ≥ 20 mm (≥ 2 cm) by chest x-ray or as ≥ 10 mm (≥ 1 cm) with CT scan, MRI, or calipers by clinical exam.

All tumor measurements must be recorded in millimeters (or decimal fractions of centimeters).

Note: Tumor lesions that are situated in a previously irradiated area might or might not be considered measurable. *If the investigator thinks it appropriate to include them, the conditions under which such lesions should be considered must be defined in the protocol.*

Malignant lymph nodes. To be considered pathologically enlarged and measurable, a lymph node must be ≥ 15 mm (≥ 1.5 cm) in short axis when assessed by CT scan (CT scan slice thickness recommended to be no greater than 5 mm [0.5 cm]). At baseline and in follow-up, only the short axis will be measured and followed.

Non-measurable disease. All other lesions (or sites of disease), including small lesions (longest diameter < 10 mm [< 1 cm] or pathological lymph nodes with ≥ 10 to < 15 mm [≥ 1 to < 1.5 cm] short axis), are considered non-measurable disease. Bone lesions, leptomeningeal disease, ascites, pleural/pericardial effusions, lymphangitis cutis/pulmonitis, inflammatory breast disease, and abdominal masses (not followed by CT or MRI), are considered as non-measurable.

Note: Cystic lesions that meet the criteria for radiographically defined simple cysts should not be considered as malignant lesions (neither measurable nor non-measurable) since they are, by definition, simple cysts.

‘Cystic lesions’ thought to represent cystic metastases can be considered as measurable lesions, if they meet the definition of measurability described above. However, if non-cystic lesions are present in the same patient, these are preferred for selection as target lesions.

Target lesions. All measurable lesions up to a maximum of 2 lesions per organ and 5 lesions in total, representative of all involved organs, should be identified as **target lesions** and recorded and measured at baseline. Target lesions should be selected on the basis of their size (lesions with the longest diameter), be representative of all involved organs, but in addition should be those that lend themselves to reproducible repeated measurements. It may be the case that, on occasion, the largest lesion does not lend itself to reproducible measurement in which circumstance the next largest lesion which can be measured reproducibly should be selected. A sum of the diameters (longest for non-nodal lesions, short axis for nodal lesions) for all target lesions will be calculated and reported as the baseline sum diameters. If lymph nodes are to be included in the sum, then only the short axis is added into the sum. The baseline sum diameters will be used as reference to further characterize any objective tumor regression in the measurable dimension of the disease.

Non-target lesions. All other lesions (or sites of disease) including any measurable lesions over and above the 5 target lesions should be identified as **non-target lesions** and should also be recorded at baseline. Measurements of these lesions are not required, but

the presence, absence, or in rare cases unequivocal progression of each should be noted throughout follow-up.

11.1.3 Methods for Evaluation of Measurable Disease

All measurements should be taken and recorded in metric notation using a ruler or calipers. All baseline evaluations should be performed as closely as possible to the beginning of treatment and never more than 4 weeks before the beginning of the treatment.

The same method of assessment and the same technique should be used to characterize each identified and reported lesion at baseline and during follow-up. Imaging-based evaluation is preferred to evaluation by clinical examination unless the lesion(s) being followed cannot be imaged but are assessable by clinical exam.

Clinical lesions: Clinical lesions will only be considered measurable when they are superficial (e.g., skin nodules and palpable lymph nodes) and ≥ 10 mm (≥ 1 cm) diameter as assessed using calipers (e.g., skin nodules). In the case of skin lesions, documentation by color photography, including a ruler to estimate the size of the lesion, is recommended.

Chest x-ray: Lesions on chest x-ray are acceptable as measurable lesions when they are clearly defined and surrounded by aerated lung. However, CT is preferable.

Conventional CT and MRI: This guideline has defined measurability of lesions on CT scan based on the assumption that CT slice thickness is 5 mm (0.5 cm) or less. If CT scans have slice thickness greater than 5 mm (0.5 cm), the minimum size for a measurable lesion should be twice the slice thickness. MRI is also acceptable in certain situations (e.g. for body scans).

Use of MRI remains a complex issue. MRI has excellent contrast, spatial, and temporal resolution; however, there are many image acquisition variables involved in MRI, which greatly impact image quality, lesion conspicuity, and measurement. Furthermore, the availability of MRI is variable globally. As with CT, if an MRI is performed, the technical specifications of the scanning sequences used should be optimized for the evaluation of the type and site of disease. Furthermore, as with CT, the modality used at follow-up should be the same as was used at baseline and the lesions should be measured/assessed on the same pulse sequence. It is beyond the scope of the RECIST guidelines to prescribe specific MRI pulse sequence parameters for all scanners, body parts, and diseases. Ideally, the same type of scanner should be used and the image acquisition protocol should be followed as closely as possible to prior scans. Body scans should be performed with breath-hold scanning techniques, if possible.

PET-CT. At present, the low dose or attenuation correction CT portion of a combined PET-CT is not always of optimal diagnostic CT quality for use with RECIST measurements. However, if the site can document that the CT performed as part of a

PET-CT is of identical diagnostic quality to a diagnostic CT (with IV and oral contrast), then the CT portion of the PET-CT can be used for RECIST measurements and can be used interchangeably with conventional CT in accurately measuring cancer lesions over time. Note, however, that the PET portion of the CT introduces additional data which may bias an investigator if it is not routinely or serially performed.

Ultrasound: Ultrasound is not useful in assessment of lesion size and should not be used as a method of measurement. Ultrasound examinations cannot be reproduced in their entirety for independent review at a later date and, because they are operator dependent, it cannot be guaranteed that the same technique and measurements will be taken from one assessment to the next. If new lesions are identified by ultrasound in the course of the study, confirmation by CT or MRI is advised. If there is concern about radiation exposure at CT, MRI may be used instead of CT in selected instances.

Endoscopy, Laparoscopy: The utilization of these techniques for objective tumor evaluation is not advised. However, such techniques may be useful to confirm complete pathological response when biopsies are obtained or to determine relapse in trials where recurrence following complete response (CR) or surgical resection is an endpoint.

Tumor markers: Tumor markers alone cannot be used to assess response. If markers are initially above the upper normal limit, they must normalize for a patient to be considered in complete clinical response. Specific guidelines for both CA-125 response (in recurrent ovarian cancer) and PSA response (in recurrent prostate cancer) have been published [JNCI 96:487-488, 2004; J Clin Oncol 17, 3461-3467, 1999; J Clin Oncol 26:1148-1159, 2008]. In addition, the Gynecologic Cancer Intergroup has developed CA-125 progression criteria which are to be integrated with objective tumor assessment for use in first-line trials in ovarian cancer [JNCI 92:1534-1535, 2000].

Cytology, Histology: These techniques can be used to differentiate between partial responses (PR) and complete responses (CR) in rare cases (e.g., residual lesions in tumor types, such as germ cell tumors, where known residual benign tumors can remain).

The cytological confirmation of the neoplastic origin of any effusion that appears or worsens during treatment when the measurable tumor has met criteria for response or stable disease is mandatory to differentiate between response or stable disease (an effusion may be a side effect of the treatment) and progressive disease.

FDG-PET: While FDG-PET response assessments need additional study, it is sometimes reasonable to incorporate the use of FDG-PET scanning to complement CT scanning in assessment of progression (particularly possible 'new' disease). New lesions on the basis of FDG-PET imaging can be identified according to the following algorithm:

- a. Negative FDG-PET at baseline, with a positive FDG-PET at follow-up is a sign of PD based on a new lesion.
- b. No FDG-PET at baseline and a positive FDG-PET at follow-up: If the positive FDG-PET at follow-up corresponds to a new site of disease confirmed by CT, this is PD. If

the positive FDG-PET at follow-up is not confirmed as a new site of disease on CT, additional follow-up CT scans are needed to determine if there is truly progression occurring at that site (if so, the date of PD will be the date of the initial abnormal FDG-PET scan). If the positive FDG-PET at follow-up corresponds to a pre-existing site of disease on CT that is not progressing on the basis of the anatomic images, this is not PD.

c. FDG-PET may be used to upgrade a response to a CR in a manner similar to a biopsy in cases where a residual radiographic abnormality is thought to represent fibrosis or scarring. The use of FDG-PET in this circumstance should be prospectively described in the protocol and supported by disease-specific medical literature for the indication. However, it must be acknowledged that both approaches may lead to false positive CR due to limitations of FDG-PET and biopsy resolution/sensitivity.

Note: A ‘positive’ FDG-PET scan lesion means one which is FDG avid with an uptake greater than twice that of the surrounding tissue on the attenuation corrected image.

11.1.4 Response Criteria

11.1.4.1 Evaluation of Target Lesions

Complete Response (CR): Disappearance of all target lesions. Any pathological lymph nodes (whether target or non-target) must have reduction in short axis to <10 mm (<1 cm).

Partial Response (PR): At least a 30% decrease in the sum of the diameters of target lesions, taking as reference the baseline sum diameters.

Progressive Disease (PD): At least a 20% increase in the sum of the diameters of target lesions, taking as reference the smallest sum on study (this includes the baseline sum if that is the smallest on study). In addition to the relative increase of 20%, the sum must also demonstrate an absolute increase of at least 5 mm (0.5 cm). (Note: the appearance of one or more new lesions is also considered progression.)

Stable Disease (SD): Neither sufficient shrinkage to qualify for PR nor sufficient increase to qualify for PD, taking as reference the smallest sum diameters while on study.

11.1.4.2 Evaluation of Non-Target Lesions

Complete Response (CR): Disappearance of all non-target lesions and normalization of tumor marker level. All lymph nodes must be non-pathological in size (<10 mm [<1 cm] short axis).

Note: If tumor markers are initially above the upper normal limit, they must normalize for a patient to be considered in complete clinical response.

Non-CR/Non-PD: Persistence of one or more non-target lesion(s) and/or maintenance of tumor marker level above the normal limits.

Progressive Disease (PD): Appearance of one or more new lesions and/or *unequivocal progression* of existing non-target lesions. *Unequivocal progression* should not normally trump target lesion status. It must be representative of overall disease status change, not a single lesion increase.

Although a clear progression of “non-target” lesions only is exceptional, the opinion of the treating physician should prevail in such circumstances, and the progression status should be confirmed at a later time by the review panel (or PI).

11.1.4.3 Evaluation of Best Overall Response

The best overall response is the best response recorded from the start of the treatment until disease progression/recurrence (taking as reference for progressive disease the smallest measurements recorded since the treatment started). The patient's best response assignment will depend on the achievement of both measurement and confirmation criteria.

For Patients with Measurable Disease (i.e., Target Disease)				
Target Lesions	Non-Target Lesions	New Lesions	Overall Response	Best Overall Response when Confirmation is Required*
CR	CR	No	CR	≥ 4 wks Confirmation**
CR	Non-CR/Non-PD	No	PR	≥ 4 wks Confirmation**
CR	Not evaluated	No	PR	
PR	Non-CR/Non-PD/not evaluated	No	PR	
SD	Non-CR/Non-PD/not evaluated	No	SD	Documented at least once ≥ 4 wks from baseline**
PD	Any	Yes or No	PD	no prior SD, PR or CR
Any	PD***	Yes or No	PD	
Any	Any	Yes	PD	

* See RECIST 1.1 manuscript for further details on what is evidence of a new lesion.

** Only for non-randomized trials with response as primary endpoint.

*** In exceptional circumstances, unequivocal progression in non-target lesions may be accepted as disease progression.

Note: Patients with a global deterioration of health status requiring discontinuation of treatment without objective evidence of disease progression at that time should be reported as “*symptomatic deterioration*.” Every effort should be made to document the objective progression even after discontinuation of treatment.

For Patients with Non-Measurable Disease (i.e., Non-Target Disease)Non-Target Lesions	New Lesions	Overall Response
--	--------------------	-------------------------

CR	No	CR
Non-CR/non-PD	No	Non-CR/non-PD*
Not all evaluated	No	not evaluated
Uequivocal PD	Yes or No	PD
Any	Yes	PD

* ‘Non-CR/non-PD’ is preferred over ‘stable disease’ for non-target disease since SD is increasingly used as an endpoint for assessment of efficacy in some trials so to assign this category when no lesions can be measured is not advised.

11.1.5 Duration of Response

Duration of overall response: The duration of overall response is measured from the time measurement criteria are met for CR or PR (whichever is first recorded) until the first date that recurrent or progressive disease is objectively documented (taking as reference for progressive disease the smallest measurements recorded since the treatment started).

The duration of overall CR is measured from the time measurement criteria are first met for CR until the first date that progressive disease is objectively documented.

Duration of stable disease: Stable disease is measured from the start of the treatment until the criteria for progression are met, taking as reference the smallest measurements recorded since the treatment started, including the baseline measurements.

11.1.6 Progression-Free Survival

PFS is defined as the duration of time from start of treatment to time of progression or death, whichever occurs first.

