5.2.1 Planned Treatment

Treatment will consist of standard of care radiation therapy to the primary tumor of the head and neck and involved nodal metastasis and draining nodal basin, as determined by treating radiation oncologist. Patients will be randomized to receive cisplatin at 100 mg/m² every 3 weeks (3 doses) during radiation versus cisplatin at 40 mg/m² once weekly (7 doses) during radiation. This will provide similar cumulative doses of cisplatin in all arms of the study.

Cisplatin Arm	Maximum Cumulative Dose
Every 3 weeks	300 mg/m ²
Weekly	280 mg/m ²

According to a recent review, total doses above 200 mg/m² during radiation lead to higher overall survival [17], and every attempt will be made to reach at least 200 mg/m². Because of the significant differences in response to therapy in oropharyngeal carcinoma (OPC) due to human papilloma virus (HPV) infection, HPV status will be recorded at baseline and adjusted during final analyses where appropriate.

Patients will first be designated by the enrolling CRA, in conjunction with the enrolling physician, as either: a) Cohort 1 (locally advanced non-nasopharyngeal SCCHN that is unresectable) OR b) Cohort 2 (resected and at high risk of recurrence with at least one of the following criteria: extracapsular nodal extension, or invasive cancer at the primary tumor resection margin (positive margin), lymphovascular invasion or perineural invasion, pT3 or pT4 primary, or the presence of multilevel nodal disease. Subjects will then be randomized to receive either Arm 1 or Arm 2 cisplatin as below.

Radiation and Cisplatin will be given concurrently and should start on the same day, \pm 1 day. Radiation will continue without interruption whenever possible. Radiation delays or interruptions will be the decision of the treating radiation oncologist, as outlined in section 5.3.

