5.6 Duration of Follow Up

Patients will be followed for 2 years after completion of chemoradiation or until death, whichever occurs first, for toxicity and PFS. Following resolution of toxicity and completion of primary endpoint assessment by PI and study team, long-term follow-up of 5 years will be performed by the Kentucky Cancer Registry. Patients removed from study for unacceptable adverse event(s) will be followed until resolution or stabilization of the adverse event.

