13. STATISTICAL CONSIDERATIONS

13.1 Study Design/Endpoints

This is a 1:1 randomized, unblinded phase II trial of radiation with cisplatin weekly versus every three weeks for patients with locally advanced non-nasopharyngeal SCCHN. The primary endpoint is cisplatin-related acute toxicities (within the first 90 days after the start of radiation). These include all grade 3-5 events of nausea/vomiting, ototoxicity, nephrotoxicity, and neutropenia and thrombocytopenia. Secondary objectives include clinical outcomes (2-year local control rates, OS, PFS, response), additional toxicity outcomes (rates of dysphagia, dry mouth, and skin, other acute and late events according to CTCAE), correlates (oxidative stress markers), and quality of life outcomes (FACTHN, FACTCOG).

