13.4 Analysis Plan

Following study completion, the percentage of subjects experiencing cisplatin-related actual toxicities in each group will be estimated along with exact 95% binomial confidence intervals. A Fisher's exact test will also be employed to test for differences between toxicity rates.

For all toxicity outcomes, incidence tables will be generated to summarize incidence of patients reporting at least one episode of each adverse event, incidence of adverse events causing withdrawals and incidence of serious adverse events. Listing of adverse events by patients will include the time to onset, the duration of each event, the severity of each event, and the relationship of the event to study therapy, whether it was a serious event, and whether it caused withdrawal.

All correlative and secondary endpoints are exploratory in nature and will be primarily descriptive; however, response and 2-year local control rates will be estimated with corresponding 95% confidence intervals and assessed for differences using Fisher's exact tests. PFS and OS will be displayed using Kaplan-Meier curves with estimated median times, and differences will be assessed using log rank tests. Repeated measures mixed models will be utilized to assess for differences in quality of life and correlative outcomes over time and between randomization groups.

In addition to those outlined above, subgroup analyses will also be run for each stratification cohort as numbers allow.

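### PFS is counted from start of treatment, so randomised patients who never start have no PFS time and the log-rank test compares starters only

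*Combined protocol and SAP*

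**What the plan says.** The only definition of PFS is in Section 11.1.6: "PFS is defined as the duration of time from start of treatment to time of progression or death, whichever occurs first".

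The surrounding text fixes the order of events:

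- **Design (Section 13.1):** "This is a 1:1 randomized, unblinded phase II trial".
- **Allocation (Section 5.2.1):** after the patient has been placed in a cohort, "Subjects will then be randomized to receive either Arm 1 or Arm 2 cisplatin as below". Treatment follows.
- **Start of treatment (Section 5.2.1):** "Radiation and Cisplatin will be given concurrently and should start on the same day", with a tolerance of one day. No maximum interval from randomisation to start is given.
- **Analysis (Section 13.4):** "PFS and OS will be displayed using Kaplan-Meier curves with estimated median times, and differences will be assessed using log rank tests". No time origin and no analysis set are named there for either endpoint.
- **Status (Section 13.4):** "All correlative and secondary endpoints are exploratory in nature and will be primarily descriptive".
- **Follow-up (Section 5.6):** "Patients will be followed for 2 years after completion of chemoradiation or until death, whichever occurs first, for toxicity and PFS".

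Section 13.7.2 does discuss who is included, but for response. It bases conclusions on eligible patients and allows those who received no study drug to be left out. It sets no rule for PFS.

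**The concern.** A randomised comparison is protected because the groups are formed by chance and everyone in them is counted. Here the PFS clock starts at an event that happens after allocation and that some patients may never reach. Such a patient has no PFS time under Section 11.1.6, and a death or progression before the first dose falls outside the definition.

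Both patient and physician know the allocated schedule, three infusions or seven, before treatment starts. A decision to decline or defer could therefore depend on the arm. If it does, and if those who do not start have a different prognosis, the two groups of starters are no longer comparable. What is at stake is the between-arm PFS comparison, one of the therapeutic comparisons listed in Section 1.2.1.

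**Working it through.** **1. Does the plan give a figure for PFS?** It does not. The sample size in Section 13.2 rests on toxicity alone: 80% against 50%, 36 per arm, Fisher's exact test, one-sided 0.05. Full enumeration of the two binomial distributions gives a power of 80.9%, against the stated 80%. The recruitment target also reproduces: 72 / (1 − 0.10) = 80. Neither figure involves the PFS origin, so changing the origin leaves both as they are.

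**2. How many patients could drop out of the comparison?** The documents give no never-start rate, so a range is assumed. Of 80 randomised patients:

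| Assumed never-start rate | Patients with no PFS time |
|---|---|
| 0% | 0 |
| 2.5% | 80 × 0.025 = 2 |
| 5% | 80 × 0.05 = 4 |
| 10% | 80 × 0.10 = 8 |

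**3. How far could the comparison move?** Assume no true difference: 2-year PFS is 60% in each arm as randomised and 30% in patients who never start. Both values are assumptions. If a proportion q of an arm never starts, the rate among its starters is

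(0.60 − q × 0.30) / (1 − q).

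- q = 0: 60.0%
- q = 0.05: (0.60 − 0.015) / 0.95 = 61.6%
- q = 0.10: (0.60 − 0.030) / 0.90 = 63.3%

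The false differences between arms, taking the three-weekly arm as the one with more non-start, are:

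| Non-start, three-weekly | Non-start, weekly | PFS in starters | False difference |
|---|---|---|---|
| 5% | 5% | 61.6% vs 61.6% | 0 |
| 10% | 5% | 63.3% vs 61.6% | 1.8 points (from unrounded rates) |
| 10% | 0% | 63.3% vs 60.0% | 3.3 points |

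The arm that loses more poor-prognosis patients looks better than it is. Swapping the arms reverses the sign.

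**4. How does that compare with chance variation?** With 40 per arm, a rate of 60% and censoring ignored, the standard error of the difference is √(2 × 0.60 × 0.40 / 40) = √0.012, or about 11 points. The largest false difference above is about 0.3 of one standard error (3.3 / 11).

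Steps 3 and 4 use 2-year PFS as a stand-in for the log-rank test. They show the order of size and are not a prediction.

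**The case against.** The case for leaving the definition alone has real substance.

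- **Both arms start at the same point.** Cisplatin begins on day 1 of radiation in each arm (Section 5.2.2), so the schedules do not themselves create a difference in start date. This stands. Any bias needs non-start or delay to differ for other reasons.
- **Early progression would seldom be seen.** The study calendar (Section 10) schedules no tumour assessment between baseline and the restaging after radiation, and Cohort 2 has been resected. This also stands. The practical loss is mainly never-starters, including any who die before the first dose.
- **The origin matches other definitions.** Best response and duration of stable disease also run from start of treatment (Sections 11.1.4.3 and 11.1.5). That is a reason to keep a treatment-based analysis as a secondary one. It does not justify it as the main between-arm comparison.
- **PFS is exploratory and unsized.** This stands and limits the consequence. A log-rank test between arms is nevertheless planned.

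Three stronger readings are not supported:

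- A reader might infer that patients will be analysed by treatment received. Nothing in the documents regroups patients who start. The narrower point is that starters are compared instead of everyone randomised.
- A reader might infer that the OS test is biased in the same way. OS has no stated origin, so the documents show a gap and no bias.
- A reader might infer that the main toxicity result is affected. The PFS definition does not enter the primary endpoint or its power.

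**Conclusion.** The point holds, at modest size. Section 11.1.6 gives a rule, and no other section restores never-starters to the PFS analysis. As written, the log-rank test compares those who started, and it could be biased if non-start differs by arm.

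Under the assumed rates the false difference in 2-year PFS runs from 0 to about 3.3 points, well inside chance variation for 40 per arm. That range rests on three assumptions that the documents do not supply: how many patients never start, how unevenly they fall between arms, and how much worse they do. With equal non-start and the same prognosis for never-starters in both arms, there is no bias in the difference. The change is worth making because it removes an avoidable weakness at very little cost. The trial's main conclusion is not threatened.

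**What to change.** 1. In Section 11.1.6, define PFS from the date of randomisation to progression or death, and in Section 13.4 state that it is analysed in all randomised patients by assigned arm.
2. State how never-starters are followed and when they are censored. Section 5.6 ties PFS follow-up to completion of chemoradiation, a date they do not have, and Sections 5.5 and 5.7 remove patients who withdraw. Without such a rule, many could be censored close to day 0 and the new origin would recover little information.
3. Keep time from start of treatment as a sensitivity analysis, and say what counts as the start. For toxicity evaluability, Section 11.1.1 uses first cisplatin and Section 13.7.1 uses first cisplatin or radiation.
4. State the same origin and analysis set for OS, as a clarification.

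The cost is a short text amendment plus survival and progression follow-up for any patient who never starts. The sample size of 80, the primary power and the visits of treated patients do not change. That the randomisation date is recorded is an assumption. The documents do not say so, and baseline windows are tied to registration, so the case report form should be checked for it. The amendment is best made before outcomes are compared by arm.
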